3. Contraindication to transfusion or history of prior severe allergic reactions to transfused blood products
4. On ECMO or in refractory shock at entry

5. Number of Subjects

This pilot aims to explore safety and measure antibody levels in patients treated with CP. We aim to enroll 30 subjects to ensure the estimate of *neutralizing antibodies* to be within 20% margin of error.

PROTOCOL TITLE: Open, non-comparative pilot study to provide access to treatment with investigational convalescent plasma and measure antibody levels in patients hospitalized with COVID-19

6. Study Timelines

Hospitalized patients will be enrolled as soon as their COVID-19 diagnosis is confirmed, using approved diagnostic methods, and will be followed until hospital discharge or death. Patient enrollment will start immediately after IRB approval. We anticipate a 3-month enrollment. The study will continue for another 24-months after the last enrollment during which we will be able to process and analyze data, and disseminate findings.

7. Study Endpoints

7.1. Primary endpoint:

- 7.1.1. Titers of SARS-CoV-2 neutralizing antibodies measured by focus reduction neutralization test (FRNT) at days 0 (pre-transfusion), 1, 3, 7 and 14 days of CP transfusion.

- 7.1.2. Availability of convalescent plasma

7.2. Secondary endpoints:

Clinical outcomes:

- 7.2.1 Serious adverse events
- 7.2.2 SARCoV-2 viral shedding in nasopharyngeal samples determined by RT-PCR
- 7.2.3 Genomic variations of SARS-CoV-2 before and after CP transfusion
- 7.2.4 Transfer to ICU
- 7.2.5 Type and duration of respiratory support (and other ICU support including ECMO, CRRT) in ICU
- 7.2.6 Cardio-circulatory arrest (at any time)
- 7.2.7 ICU mortality and LOS
- 7.2.8 Hospital mortality and LOS
- 7.2.9 Ventilator-free days
- 7.2.10 In hospital mortality
- 7.2.11 Titer of other functions of antibodies, including antibody-dependent cell-mediated and complement-dependent cytotoxicity

7.3. Safety Endpoints:

- 7.3.1 Rapid deterioration of respiratory or clinical status on transfusion of SARS-CoV-2 convalescent plasma.
- 7.3.2 Cumulative incidence of serious adverse events during the study period: febrile non-hemolytic transfusion reaction, allergic transfusion reaction, transfusion related acute lung injury (TRALI), transfusion associated circulatory overload (TACO),

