Our primary endpoint for statistical analysis is changes in NAb titers at day 1, 3, 7, and 14 from the entry level (day 0). Our primary hypothesis is that NAb titers will increase post-transfusion in positive correlation with transfused volume of convalescent plasma when adjusted for NAb titer in the convalescent plasma. We will use repeated measurements analysis of variance (ANOVA) or analysis of covariance (ANCOVA) when controlling for other factors (e.g. use of hydroxychloroquine) for initial exploration of the association with the transfusion volume of convalescent plasma. A more advanced approach is to use nonlinear regression models with random effects to characterize the trajectory of NAb titers over the course of 14 days. This latter approach can effectively characterize individual-specific trajectory in NAb titers in relation to convalescent plasma, and at the same time quantify between-patients variation, thereby improving statistical power. This mixed-effects nonlinear regression modeling approach is also capable of adjusting for other factors as appropriate (e.g. patient age). We will also conduct post-hoc analysis of change in NAb titers from day 0 to a specific day (day 1, 3, 7, or 14) post transfusion of convalescent plasma when appropriate. Better understanding and better characterization of the relationship between NAb titers and amount of convalescent plasma transfusion adjusted for NAb titer in the convalescent plasma will inform standardized dosage for future study.

In the absence of a comparison group, we will use descriptive statistics to report other parameters of interest (e.g. secondary outcomes), including the use of mean (SD), frequency (%) and their confidence interval. When appropriate, we will also report association between a parameter of interest and a factor of clinical relevance (e.g. duration of shading and underlying comorbidities, NAb titers at a specific post-transfusion day and underlying comorbidities, NAb titers at a specific post-transfusion day and secondary outcomes such as transfer to ICU or hospital death). This analysis will utilize odds ratio and Fisher's test for dichotomous variables, and Wilcoxon test a continuous variable.

We will conduct interim analysis after the first 10 patients complete the study. Based on the interim analysis results we may consider submitting a protocol amendment requesting adjustment our patient recruitment or CP dosing.

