a. If available published information convincingly reports non-efficacy or significant safety concerns with the use of SARS-CoV-2 convalescent plasma.

b. If an unexpectedly high incidence of serious adverse events judged to be related to SARS-CoV-2 convalescent plasma is detected in these critically ill COVID-19 patients during the trial in the clinical judgement of the investigators compared to that expected in similarly ill patients receiving normal donor plasma in the clinical judgement of the investigators.

PROTOCOL TITLE: Open, non-comparative pilot study to provide access to treatment with investigational convalescent plasma and measure antibody levels in patients hospitalized with COVID-19

- c. If there is an unanticipated safety signal, stopping the study will be considered.

14.7. Findings will be reported to the HRRC within 5 business days and to the FDA accordingly. A preliminary analysis of the study end points will be performed after 10 patients have been enrolled and end-points reached. The results will be presented to the HRRC and investigators.

15. Withdrawal of Subjects

15.1. Subjects will be withdrawn if the PI determines, in consultation with the treating clinician(s) that continuation in the study is not in the participant's best interest. Subjects may also withdraw (or be withdrawn by their LAR at their request at any time during their participation in the study by contacting a member of the study team.

15.2. If a patient develops a serious adverse event that may be probably or definitely related to the CP, during the infusion, that may trigger the discontinuation of the offending drug.

15.3. If a participant is withdrawn from the study, chart review will continue to be performed to track the participant's clinical outcomes.

15.4. Data and specimens collected before withdrawal will not be removed from the study.

16. Data Management/Confidentiality

16.1. Participants will be assigned a randomly generated study ID that will be linked to identifiers (MRN, DOB) in a linking table to be kept separate from the research data. Data and specimens will be labelled with the study ID only.

16.2. Only HRRC-approved members of the study team who have the appropriate training will have access to the data and identifiers.

16.3. Data will be entered into REDCap on a password-protected computer using a secure network.

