A key potential benefit is treatment for established infection. Convalescent plasma would be administered to those with clinical disease in an effort to reduce their symptoms and mortality. Based on the historical experience with antibody administration, it can be anticipated that *antibody administration relatively early in the course of disease would be more effective in preventing disease progression than in the treatment of established severe disease.*

Given that historical and current anecdotal data on use of convalescent plasma suggest it is safe in coronavirus infection, the high mortality of COVID-19, particularly in elderly and vulnerable persons, suggests that the benefits of its use in those at high risk for or with early disease outweigh the risks. However, for all cases where convalescent plasma administration is considered, a risk-benefit assessment must be conducted to assess individual variables.

20. Recruitment Methods

Members of the research team will review the list of admitted or hospitalized patients with a positive SARS-CoV-2 test. Alternatively, treating providers may also notify the research team of the admission of SARS-CoV-2 patients or the positive result of a suspected COVID-19 patient.

21. Provisions to Protect the Privacy Interests of Subjects

- 21.1.** Only members of the research team will access trial related documents.
- 21.2.** All study procedures will be conducted in the participant's room or other private area of the hospital.

22. Economic Burden to Subjects

PROTOCOL TITLE: Open, non-comparative pilot study to provide access to treatment with investigational convalescent plasma and measure antibody levels in patients hospitalized with COVID-19

- 22.1. The study is responsible for the cost of any research-related procedures. The participant and/or third party payer is responsible for any standard of care procedures.
- 22.2. Investigators do not anticipate any additional costs.

23. Compensation

No compensation will be given to study participants.

24. Compensation for Research-Related Injury

The University of New Mexico does not have funds set aside to pay for the cost of any care or treatment that might be necessary or for any wages lost as a result of participating in this study. Medical costs to care and treatment of study related harm will be billed to the participant and/or third party payer.

25. Consent Process

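### Section 13.2 relates day-7 and day-14 NAb titers to hospital death, but those titers appear to exist only for patients still admitted, so the association can be biased in an unknown direction

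*Combined protocol and SAP*

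**What the plan says.** Among the associations to be reported where appropriate, section 13.2 names "NAb titers at a specific post-transfusion day and secondary outcomes such as transfer to ICU or hospital death". The method is given in one sentence: "This analysis will utilize odds ratio and Fisher's test for dichotomous variables, and Wilcoxon test a continuous variable".

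Section 7.1.1 schedules titers "at days 0 (pre-transfusion), 1, 3, 7 and 14 days of CP transfusion", and Table 1 in section 12 lists the same days. Section 6 says patients "will be followed until hospital discharge or death". Section 21.2 adds: "All study procedures will be conducted in the participant's room or other private area of the hospital".

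The outcome does not depend on a blood sample. It is listed as "7.2.10 In hospital mortality", and for withdrawn participants section 15.3 says "chart review will continue to be performed to track the participant's clinical outcomes". Section 13 gives no rule for titers that are absent because the patient has left hospital or died.

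**The concern.** Death in hospital is known for every patient. A titer on day 7 or 14, read from sections 6 and 21.2 together, is known only for those alive and still in a bed that day. The day-14 comparison therefore sets patients who died after day 14 against survivors who stayed beyond day 14. Every faster recovery and every earlier death is left out.

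Leaving patients out is harmless if titer has nothing to do with length of stay. If it does, the remaining survivors are selected on titer while the remaining deaths are not selected in the same way, and a difference can appear where titer has no effect on death. Higher titer with earlier discharge makes the remaining survivors low-titer, so high titer seems to go with death. Higher titer with later discharge produces the reverse.

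The Background section asks whether titers are associated with clinical outcomes, and section 7.3.2 lists antibody-dependent enhancement as a safety endpoint. Readers will look at this association, and a spurious pattern of either sign could be misread as harm or as benefit.

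**Working it through.** **The plan's own figure.** Section 5 says "We aim to enroll 30 subjects to ensure the estimate of" neutralizing antibodies to within a 20% margin. No SD, CV or confidence level is given, so 30 cannot be reproduced uniquely. For a mean at 95% confidence, 1.96 × CV / √30 ≤ 0.20 requires CV ≤ 0.20 × √30 / 1.96 = 0.56. No figure is given for the titer-death association, so its distortion has to be explored under assumptions.

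**Main model. All inputs are assumptions.** S is severity and A is the patient's own antibody level. Both are standard normal and independent.

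- Death: logit P = −2.2 + 1.2·S, about 15% of patients, or 0.15 × 30 = 4.5 deaths. Titer has no effect on death.
- Survivors' discharge day: 7·exp(0.5·S − b·A + 0.5·e), with e standard normal. One SD more antibody multiplies the stay by exp(−b): 0.82 at b = 0.2 and 0.61 at b = 0.5.
- Day of death: lognormal, median 12, log-SD 0.6.
- A titer exists on day L only if discharge or death comes after L.

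The measure is mean A in later deaths minus mean A in survivors, among patients with a titer. The true titer effect is zero.

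| Day | b = 0.2 | b = 0.35 | b = 0.5 | Survivors with titer (of 30) | Later deaths with titer |
|---|---|---|---|---|---|
| 1 | 0.00 | 0.01 | 0.02 | about 25 | 4 to 5 |
| 3 | 0.07 | 0.13 | 0.19 | 21 to 22 | 4 to 5 |
| 7 | 0.24 | 0.39 | 0.51 | about 12 | 3.6 |
| 14 | 0.45 | 0.69 | 0.86 | 3 to 5 | 1.8 |

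Differences are in SD units. At b = 0 they are about zero on every day. Reversing the sign of b reverses the result: b = −0.35 gives −0.39 SD on day 7 and about −0.7 SD on day 14.

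**As a test in 30 patients.** At two-sided 0.05 and before any FDR adjustment, a significant result in the false direction occurs in about 4 to 10% of trials on day 7 and under 3% on day 14, against a nominal 2.5%. In about 17% of trials no day-14 test is possible, because one group is empty.

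**Second model, different assumptions.** Here 25% die, survivors' median stay is 10 days, median time to death is 12 days, log-SD is 0.7, and rho is the correlation of titer with log stay in survivors. AUC is the chance that a death has a higher titer than a survivor, and its true value is 0.50.

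- rho −0.2 to −0.6: AUC 0.53 to 0.59 on day 7 and 0.56 to 0.70 on day 14.
- rho 0: AUC 0.50 throughout.
- rho +0.2 to +0.6: day-14 AUC 0.44 down to 0.30.
- Day 1: AUC 0.50 throughout.

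About 21.5 of 30 patients have a day-7 titer and 10 a day-14 titer, with 5.8 and 3.1 later deaths among them. A falsely significant day-14 result rises from about 2% to 7 to 11% at rho −0.4 to −0.6.

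**Competing-hazards variant.** Selection mostly pulled an existing association toward 0.50 without reversing it: AUC 0.422 overall became 0.457 on day 14 when titer speeds discharge, and 0.625 became 0.583 when sicker patients have higher titers.

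**Is day 1 clean?** It is clean of discharge selection only. If A and S correlate at 0.3 in the main model, with titer still having no effect on death, the day-1 difference is +0.30 SD. At b = 0 it is +0.13 on day 7 and about 0 on day 14. That is confounding by severity, a separate problem.

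**The case against.** The strongest reply is that the plan already limits this analysis. It is an example, done only where appropriate. The closing paragraph of section 13.2 admits that power and data depth are lacking, calls much of the secondary work exploratory, and applies FDR. No stopping rule in section 14.6 names a titer-outcome association. With two or three deaths on day 14, little would be concluded anyway. This stands as a limit on severity. It does not answer the point, because FDR and an exploratory label do not change who enters the comparison.

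The premise is also partly inferred. Table 1 lists days 7 and 14 without making them conditional on admission, and the text between sections 9.1.2 and 12.1 was not available here. If blood is drawn after discharge, most of the concern falls away.

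Three stronger readings are tempting and not supported:

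- A reader might infer that the analysis will produce a false signal of harm. That needs higher titer to go with earlier discharge, which no section states. The opposite sign, simple dilution or no bias are all open.
- A reader might infer that most survivors are lost by day 7. Under the main model about 12 of 25 remain, roughly half. Only on day 14 are most lost.
- A reader might infer that a day-1 titer gives an unbiased answer. It avoids discharge selection but not confounding by severity.

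**Conclusion.** The structural point holds. As written, section 13.2 allows tests of day-7 and day-14 titers against hospital death in a sample restricted, apparently, to patients still admitted, and nothing in section 13 deals with that restriction. The bias has unknown direction and is absent if titer is unrelated to time to discharge.

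Under the main assumptions with |b| from 0.2 to 0.5, its size is about 0.2 to 0.5 SD on day 7 and 0.4 to 0.9 SD on day 14. It is at most 0.2 SD on day 3 and about zero on day 1. Mortality, length of stay and the titer-stay link are all assumed. The day-0 comparisons in section 13.2 are unaffected, because the baseline sample precedes any discharge from follow-up.

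With so few later deaths, a distorted estimate is a greater risk than a significant test. This is a modest point about an exploratory analysis, worth correcting because the correction is cheap.

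**What to change.** In section 13.2:

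- Test hospital death and the other in-hospital outcomes against the day-1 titer, when almost all patients are still admitted. State that the association is unadjusted for severity and not causal.
- Report day-7 and day-14 titers by outcome descriptively, without a test. Give the numbers still in hospital, discharged and dead on each day, and say that the results apply only to patients still admitted.
- Day 3 may be kept as a sensitivity analysis with the same counts.
- State whether samples are drawn after discharge. If they are, say so in section 6 and Table 1.

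Only wording changes; the sampling schedule stays as it is. The cost is that later titers are no longer formally tested against outcomes. On day 14 those tests would have rested on about two deaths under the main model and three under the second. A landmark analysis with discharge as a competing event and adjustment for severity is an alternative, but 30 patients give it little to work with.

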35. CHECKLIST SECTION

This section contains checklists to provide information on a variety of topics that require special determinations by the IRB. Please complete all checklists relevant to your research.

36. Partial Waiver of Consent for Screening/Recruitment

Complete this checklist if you are requesting a partial waiver of consent so that you can review private information to identify potential subjects and/or determine eligibility prior to approaching potential subjects for consent or parental permission.

A. Describe the data source that you need to review (e.g., medical records):

Medical Record

B. Describe the purpose for the review (e.g., screening):

Screening and Recruitment

C. Describe who will be conducting the reviews (e.g., investigators, research staff):

Principal Investigator with other members of the study team

D. Do all persons who will be conducting the reviews already have permitted access to the data source?

Yes

No. Explain:

i. Verify that each of the following are true or provide an alternate justification for the underlined regulatory criteria:

1. The activity involves no more than minimal risk to the subjects because the records review itself is non-invasive and the results of the records review will not be used for any purposes other than those described above.

True

Other justification:

2. The waiver or alteration will not adversely affect the rights and welfare of the subjects because eligible subjects will be approached for consent to participate in the research and are free to decline. Further, the information accessed during the records review will not be disclosed to anyone without a legitimate purpose (e.g., verification of eligibility).

PROTOCOL TITLE: Open, non-comparative pilot study to provide access to treatment with investigational convalescent plasma and measure antibody levels in patients hospitalized with COVID-19

True

Other justification:

3. The research could not practicably be carried out without the waiver or alteration because there is no other reasonably efficient and effective way to identify who to approach for possible participation in the research.

True

Other justification:

4. Whenever appropriate, potentially eligible subjects will be presented with information about the research and asked to consider participation. (Regulatory criteria: Whenever appropriate, the subjects will be provided with additional pertinent information after participation.)

True

Other justification:

37. Partial Waiver of HIPAA Authorization for Screening/Recruitment

Complete the following additional questions/attestations if the records you will review to identify potential subjects and/or determine eligibility include Protected Health Information (PHI).

A. Will you be recording any PHI when conducting the records review to identify potential subjects and/or determine eligibility?

Yes. Describe:

No

B. If you answered "Yes" to question 6 above, please describe when you will destroy identifiers (must be the earliest opportunity consistent with the conduct of the research) or provide justification for why they must be retained:

C. The PHI accessed or recorded for identification/screening purposes will not be reused or disclosed to (shared with) any other person or entity, except as required by law, for authorized oversight of the research study, or for other research for which the use or disclosure of the PHI would be permitted under the Privacy Rule.

True

PROTOCOL TITLE: Open, non-comparative pilot study to provide access to treatment with investigational convalescent plasma and measure antibody levels in patients hospitalized with COVID-19

False

38. Waiver of Documentation of Consent N/A

39. Alteration of Consent N/A

40. Full Waiver of Consent/Parental Permission N/A

41. Full Waiver of Consent/Parental Permission (Public Benefit or Service Programs) : N/A

42. Full Waiver of HIPAA Authorization (Checklist) N/A

43. Other Waiver Types (Checklist):N/A

44. Vulnerable Populations (Checklist)

A. Adults with Cognitive Impairments

Complete this checklist if the subject population will include adults with cognitive impairments.

This checklist does not need to be completed if the research doesn't involve interactions or interventions with subjects and will be conducted under a waiver of consent.

1. Describe why the objectives of the study cannot be met without inclusion of adults with cognitive impairments.

COVID-19 infection may affect persons with pre-existing cognitive impairment for whom no SOC treatment exists. COVID-19 infection can cause conditions resulting in cognitive impairment.

2. Describe how capacity to consent will be evaluated.

By the research team in consultation with clinical care provider, by capacity to consent quiz or by the teach back technique.

3. If subjects may regain capacity to consent, or if subjects may have fluctuating capacity to consent, describe your plans to evaluate capacity to consent throughout the research and to obtain consent to continue participation if capacity is regained.

Capacity to consent will be assessed as part of the ongoing consent process. To protect their rights and welfare, consent will be sought from competent LAR, and participants who regain capacity to consent as (determined by the study team in consultation with clinical care providers) will be re-consented.

PROTOCOL TITLE: Open, non-comparative pilot study to provide access to treatment with investigational convalescent plasma and measure antibody levels in patients hospitalized with COVID-19

4. Describe your plans, if any, to provide information about the research to subjects and the steps you will take to assess understanding.

The investigators will utilize the Capacity to Consent Quiz with the consent form. After the consent form has been discussed with the participant, the investigator will administer the Capacity to Consent Quiz or by teach back technique after each section of the consent. Based on the results, the investigators will determine if the participant or LAR has the ability to consent.

5. Describe your plans to obtain assent, including whether assent will be obtained from none, some, or all subjects.
6. Describe why risks to subjects are reasonable in relation to anticipated benefits to the subjects.

There is no SOC treatment for COVID-19 infection

7. If this study involves a health or behavioral intervention, describe why the relation of the anticipated benefit to the risk of the research is at least as favorable to the subjects as that presented by alternative procedures.

There is no SOC treatment for COVID-19 infection

8. Describe your plans for monitoring the well-being of subjects including any plans to withdraw subjects from the research if they appear to be unduly distressed.

All COVID-19 patients enrolled in this study will be hospitalized and closely monitored. Treating providers and members of the research team will be attentive to the clinical condition of all subjects.

- B. Children N/A
- C. Pregnant Women and Fetuses N/A
- D. Neonates of Uncertain Viability or Nonviable Neonates N/A
- E. Nonviable Neonates N/A
- F. Biomedical and Behavioral Research Involving Prisoners N/A

45. Medical Devices (Checklist) N/A

46. Export Control (Checklist) N/A

47. Data Transfer/Sharing (Checklist)

PROTOCOL TITLE: Open, non-comparative pilot study to provide access to treatment with investigational convalescent plasma and measure antibody levels in patients hospitalized with COVID-19

Complete this checklist if the research involves transferring/sharing of data with an external entity (institution, company, etc.).

A. Will data be transferred/shared with an external entity (institution, company, etc.)?

Yes

No. **The remainder of this section does not apply.**

B. Indicate if the data is incoming and/or outgoing:

C. Provide the name of the entity that data will be transferred/shared with:

D. Provide the contact name, email and phone number with whom data is being transferred/shared with:

E. Who is responsible for transmission of the data?

F. Who is responsible for receiving the data?

G. Describe how the data will be transferred/shared. Please note data cannot be transferred/shared without assistance from UNM HSC IT. **Requesting HSC Central IT Transfer is detailed on the Sponsored Projects website:**

H. For data being transferred/shared with outside locations or entities, describe the following:

- Where is data storage and how will it be maintained in a secure manner (i.e. encryption, password protection, use of Qualtrics or REDCap, etc)?
- What is method in which data will be collected and stored (i.e. electronic, hard copy, etc)?
- How long will the data be stored?
- Who will have access to data?

I. Please list all specific data elements, variables, etc. to be sent out and/or received.

Indicate if the data contains identifiers and health information. Please note that identifiers that MUST be removed to make health information de-identified are as follows: Names, All geographic subdivision smaller than a State, All elements of year (except year), Telephone, Fax numbers, E-mail addresses, Social Security, Medical record number, Health plan beneficiary, Account numbers, Certificate/license numbers, Vehicle identifiers and serial numbers, Device identifiers and serial numbers, Web URLs, IP address numbers, Biometric identifiers, full face photographic images, and Any other unique identifying number, characteristic or code.)

J. If the research requires the access, use, or disclosure of any of the 18 individually identifiable protected health information (PHI) identifiers that can be used to identify, contact, or locate a person (e.g., name, medical record number, etc.), are the subjects going to consent to or authorize the disclosure of their individually identifiable health information?

a. **Or** is HIPAA authorization altered or waived?

K. What is the classification of the data (de-identified, limited data set, protected health information, other).

PROTOCOL TITLE: Open, non-comparative pilot study to provide access to treatment with investigational convalescent plasma and measure antibody levels in patients hospitalized with COVID-19

- L. Does the request to transfer/share data include clinical data that belongs to the UNM Health Systems?
- M. Does the data to be transferred/shared include information about patients seen at external health systems or at a third party medical provider?
- N. Is the external entity a “covered entity”?
- O. Is the data that is going to be transferred/shared owned or partially owned by another party or have any type of restrictions including regulatory restrictions (i.e. HIPAA, FERPA, etc.)?
- P. Is the data publically available? If yes, please provide details:
- Q. Does the data include information about substance abuse treatment, sexually transmitted diseases, genetic testing results, HIV/AIDS testing results, and/or mental health?

48. Specimen Transfer/Sharing (Checklist)

Complete this checklist if the research involves transferring/sharing of specimens with an external entity (institution, company, etc.).

- A. Will specimens be transferred/shared with an external entity (institution, company, etc.)?

Yes

X No. The remainder of this section does not apply.

- B. Indicate if the specimens are incoming and/or outgoing:
- C. Provide the name of the entity that specimens will be being transferred/shared with:
- D. Provide the contact name, email and phone number with whom specimens are being transferred/shared with:
- E. Who is responsible for sending out the specimens? Please note specimens cannot be sent out without a fully executed material transfer agreement. [name]
- F. Who is responsible for receipt of the specimens? Please note specimens cannot be received without a fully executed material transfer agreement.
- G. For specimens being transferred/shared with outside locations or entities, describe the following:
